7.4. Dose Adjustment for 5FU and Irinotecan Toxicities

A cycle is 4 weeks – with treatment on days 1 and 15. We do not make up day #15 treatments if a patient should require adjustment or omission based on outlined criteria below.

- This study will take into consideration previous toxicities experienced with FOLFIRI prior to enrollment. The initial dose of FOLFIRI will be determined by the investigator at time of trial initiation. Prior to enrollment, if the patient experienced significant toxicity with FOLFIRI and dose adjustments were required, these dose adjustments will continue upon initiation of this trial.
- For toxicities which are considered by the investigator unlikely to develop into serious or life-threatening events (e.g. alopecia, altered taste etc.), treatment will be continued at the same dose without reduction or interruption. In addition, no dose reductions or interruptions will be required for anemia as it can be satisfactorily managed by transfusions.
- For any event that is apparent at baseline, the dose modifications will apply according to the corresponding shift in toxicity grade, if the investigator feels it is appropriate. (e.g. if a patient has grade 1 asthenia at baseline which increases to grade 2 during treatment, this will be considered as a shift of 1 grade and treated as a grade 1 toxicity for dose modification purposes).
- If on the first day of chemotherapy treatment, the granulocyte count (ANC) is < 1,500 or the platelet count is < 75,000, treatment will be held for up to three weeks until ANC is ≥ 1200 and platelet count is ≥ 75,000. CBC should be obtained at least weekly when treatment is held. Chemotherapy doses will not be reduced based on nadir counts except in febrile neutropenia as defined below.
- If the dose is modified to manage an adverse event, it is recommended that the patient be seen by the investigator prior to re-starting study drug.
- If a rest period is extended due to toxicity, the "complete" cycle should be given afterwards with chemotherapy and panitumumab. If toxicity requires a dosing delay/interruption of both 5-FU and irinotecan of more than six weeks or at the

discretion of the investigator, the patient will be withdrawn from the study for toxicity reasons.

Table 1: Dose modifications during a course of therapy (day #15 of each cycle).

- Dose adjustments for hematological toxicity during a course of therapy are based on the blood counts obtained in preparation for that day of treatment.

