- All dose adjustments are relative to dose given at on day #1 of that cycle.

FOLFIRI Regimen Dose Modification Guideline^a

Dose Modifications for the Next Cycle Based on the Worst Toxicity Observed ^{b,f}		
Toxicity Grade ^b (CTCAE v4.0)	5-FU bolus and continuous infusion	Irinotecan
Neutropenia, Thrombocytopenia, and Leukopenia (since prior treatment)		
0 or 1	Maintain dose level	Maintain dose level
2	Discontinue 5-FU bolus	Maintain dose level
3	Discontinue 5-FU bolus and ↓ 1 dose level continuous infusion	↓ 1 dose level
4	Discontinue 5-FU bolus and ↓ 2 dose levels continuous infusion	↓ 2 dose levels
Neutropenic fever or infection ^c	Discontinue 5-FU bolus and ↓ 2 dose levels continuous infusion	↓ 2 dose levels
Diarrhea ^d (since prior treatment)		
0 or 1	Maintain dose level	Maintain dose level
2	Discontinue 5-FU bolus and ↓ 1 dose level continuous infusion	Maintain dose level
3	Discontinue 5-FU bolus and ↓ 1 dose level continuous infusion	↓ 1 dose level
4	Discontinue 5-FU bolus and ↓ 2 dose levels continuous infusion	↓ 2 dose levels
Mucositis/Stomatitis (since prior treatment)		
0, 1 or 2	Maintain dose level	Maintain dose level
3	Discontinue 5-FU bolus	Maintain dose level
4	Discontinue 5-FU bolus and ↓ 1 dose level continuous infusion	Maintain dose level
Vomiting (since prior treatment)		
0, 1 or 2	Maintain dose level	Maintain dose level
3	Maintain dose level	↓ 1 dose level
4	Discontinue 5-FU bolus ↓ 1 dose level continuous infusion	↓ 1 dose level

Palmar-plantar erythrodysesthesia			
0, 1 or 2	Maintain dose level	Maintain dose level	
3	Discontinue 5-FU bolus ↓ 1 dose level continuous infusion	Maintain dose level	
Other nonhematologic toxicities (except alopecia and skin-related toxicities) ^e			
0, 1 or 2	Maintain dose level	Maintain dose level	
3	Discontinue 5-FU bolus ↓ 1 dose level continuous infusion	↓ 1 dose level	
4	Discontinue 5-FU bolus ↓ 2 dose levels continuous infusion	↓ 2 dose levels	

^a There will be no leucovorin dose reduction. If 5-FU bolus dropped, leucovorin will be discontinued as well.

^b NCI CTCAE(Version 4.0) (Appendix E)

^c Absolute Neutrophil Count <1000/mm³ and Temperature ≥ 38.5°C

^d Despite maximum supportive care

^e Bilirubin grade 3 and grade 4 hold dose: once the bilirubin level has resolved to ≤ grade 1 a dose reduction for 5-FU and irinotecan is required.

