^f If the patient's starting dose upon enrollment is not full dose FOLFIRI, future dose adjustments will be made as to reflect the starting dose (i.e. proceed to the next recommended dose)

*There will be no leucovorin dose reduction. If bolus 5-FU dose omitted, leucovorin is also omitted

Table 2. FOLFIRI Regimen Dose Levels (mg/m²)

DRUG	Starting Dose (mg/m ²)	Dose Level -1 (mg/m ²)	Dose Level -2 (mg/m ²)	Dose Level -3 (mg/m ²)
Irinotecan	180	150	120	Discontinue
5-FU 46 hour infusion	2400	2000	1600	Discontinue

7.5. Panitumumab Dose Modification for Toxicity- (Please refer to Table 3).

The starting panitumumab dose is 6 mg/kg every 2 weeks. The total dose may be rounded up or down by no greater than 10 mg. The panitumumab dose will be calculated based on the subject's actual body weight at baseline and will not be re-calculated unless the actual body weight changes by at least 10%. Panitumumab will be diluted in a minimum of 100 mL of pyrogen-free 0.9% sodium chloride solution USP/PhEur (normal saline solution, supplied by the site). The maximum concentration of the diluted solution to be infused should not exceed 10 mg/mL. The

volume of normal saline should be increased as needed to ensure the maximum concentration of the diluted solution does not exceed 10 mg/mL. Panitumumab will be administered IV by an infusion pump through a peripheral line or indwelling catheter using a 0.22-micron in-line filter infusion set-up over 1 hour ± 15 minutes by a trained healthcare professional. If the first infusion is well tolerated (ie without any serious infusion-related reactions) all subsequent infusions may be administered over 30 ± 10 minutes. In the event a subject's actual weight requires greater than 150 mL volume infusion, panitumumab will be administered over 60 to 90 minutes ± 15 minutes, as tolerated.

The bag should be labeled per site pharmacy Standard Operating Procedures and promptly forwarded to the clinical research center for infusion.

The effects of overdose of panitumumab are not known.

See Appendix 6 Pharmacy Guide for information on panitumumab packing and formulation, labeling, storage, preparation, supply/return, and accountability.

Pre-medication for Panitumumab

Panitumumab specific pre-medication is not required for routine panitumumab infusions. If, during or after any infusion, a reaction occurs, pre-medication may be used for subsequent panitumumab infusions according to institutional guideline or investigator's discretion.

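### Section 7.4 gives two conflicting FOLFIRI dosing rules for a known low blood count without fever: the text keeps the dose, the dose-modification grid cuts it

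*Combined protocol and SAP*

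**What the plan says.** Three statements in section 7.4 bear on the chemotherapy dose after a low blood count.

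- The general bullets rule out nadir-based reductions, with one exception: "Chemotherapy doses will not be reduced based on nadir counts except in febrile neutropenia as defined below".
- A bullet under the Table 1 caption, which is limited to day 15 of each cycle, says: "Dose adjustments for hematological toxicity during a course of therapy are based on the blood counts obtained in preparation for that day of treatment".
- The grid that follows is headed "Dose Modifications for the Next Cycle Based on the Worst Toxicity Observed". Its cytopenia block is labelled "Neutropenia, Thrombocytopenia, and Leukopenia (since prior treatment" and requires action at grades 2, 3 and 4. A separate row covers "Neutropenic fever or infection", which footnote c defines as ANC below 1000/mm³ with a temperature of at least 38.5°C.

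Table 2, "FOLFIRI Regimen Dose Levels", sets irinotecan at 180, 150 and 120 mg/m² and infusional 5-FU at 2400, 2000 and 1600 mg/m², then stops both. The 5-FU bolus is 400 mg/m² (section 7.2).

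**The concern.** The first statement says a low count between doses does not change the dose unless the patient was febrile. The grid says the worst count in that interval does change it. Both are operative instructions, and no text ranks them.

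Section 3.2 names two participating institutions. With the same known afebrile count, one could give full dose and the other a reduced dose on day 1 of the next cycle. Each could cite section 7.4, and it would be unclear which was the deviation. Under the grid, the dose would also depend on whether somebody happened to draw an extra count. At stake is consistent and safe dosing of individual patients.

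**Working it through.** **1. Does the fever exception reconcile the rules?** No. Neutropenic fever has its own row and definition, so the graded cytopenia rows apply to patients without fever. Those are the patients whose dose the nadir sentence protects.

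**2. Does the treatment-day bullet reconcile them?** Only in part. For day 15, the bullet and the nadir sentence agree, and only the look-back label on the cytopenia rows disagrees. For day 1 of the next cycle, the bullet's caption does not reach, while the grid's heading names the next cycle explicitly. There the nadir sentence and the grid conflict directly.

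**3. How far apart are the doses?** Take a patient on full dose with a known afebrile low count that has recovered by day 1. The text gives total 5-FU of 400 + 2400 = 2800 mg/m² and irinotecan 180 mg/m² at every grade. The grid gives:

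| Worst grade | 5-FU (no bolus) | Change in total 5-FU | Irinotecan | Change |
|---|---|---|---|---|
| 2 | 2400 | 2400/2800 = 0.857, -14% | 180 | none |
| 3 | 2000 | 2000/2800 = 0.714, -29% | 150 | 150/180 = 0.833, -17% |
| 4 | 1600 | 1600/2800 = 0.571, -43% | 120 | 120/180 = 0.667, -33% |

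The grade 4 row matches the neutropenic-fever row. Leucovorin also stops whenever the bolus stops (footnote a).

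**4. When can it arise?** Doses are 14 days apart. Sections 6.4 and 6.5 schedule counts only in the 48 hours before days 1 and 15, which is 14 - 2 = 12 to 14 days after the previous dose. Section 1.2.2.2 places the lowest white counts after a first fluorouracil course at days 9 to 14, so days 9 to 11 have no scheduled count. The documents give no nadir timing for irinotecan. Two sources of a conflicting count remain: unscheduled draws, and the counts that section 7.4 requires at least weekly during a hold, which may fall below the one that caused the hold. Section 7.7.3 allows growth factor for a prolonged ANC below 500. That presumes repeat counts in some patients but schedules none. No frequency is given.

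**5. A related wrong dose level.** In section 7.5, the re-escalation bullet for patients at 50% panitumumab offers a 60% dose as the alternative. Table 3 lists only 100%, 80% and 50% (6, 4.8 and 3.0 mg/kg). A 60% dose would be 0.60 × 6 = 3.6 mg/kg, which is not a protocol level.

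**The case against.** The best defence is that a specific prohibition limits a general grid. The nadir sentence is mandatory. It points forward to the febrile neutropenia definition, which sits in the grid's own footnotes, so its author had the grid in view. The grid is titled a guideline, and its look-back label is generic, appearing also on the diarrhea, mucositis and vomiting blocks. This reading is plausible and leads to the dosing recommended below. But it leaves the look-back and worst-toxicity wording without effect on the cytopenia rows, and the protocol never states it.

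A second defence is structural. The grid has no number and the next table is Table 2, so the grid may itself be Table 1, with the treatment-day bullet as its note. That is a fair reading, but it exposes another mismatch: the caption confines the table to day 15 while the heading speaks of the next cycle.

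It is also true that the mandatory review teleconferences in section 9.3 can catch individual cases. They do not say which rule governs.

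A reader might go further and infer that the grid would stop chemotherapy in patients who enter on reduced doses. Section 7.4 says of earlier reductions that "these dose adjustments will continue upon initiation of this trial", and two levels down from level -1 lands on discontinuation in Table 2. The documents do not support that as a firm result. Section 7.2 exempts several sub-optimally controlled toxicities, neutropenia among them, from carry-over and asks for full-dose irinotecan. Footnote f says "future dose adjustments will be made as to reflect the starting dose (i.e. proceed to the next recommended dose", which can mean a single step.

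**Conclusion.** The conflict is real but narrow. It is a dosing-instruction correction between minor and should-fix. For the same known afebrile count in a full-dose patient, section 7.4 supports doses that differ by up to 43% in total 5-FU and 33% in irinotecan. These are per-patient differences. They assume that an interim or hold-period count exists, and the documents do not say how often that happens.

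A reader might infer that the ambiguity undermines the trial's efficacy result. Nothing in the documents shows this. The sample size, the error rates and the Kaplan-Meier analysis of PFS do not depend on which rule is used, and in a single-arm trial there is no between-arm comparison to bias.

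**What to change.** One short amendment to sections 7.4 and 7.5:

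- **(a) Cytopenia rows.** Replace the look-back label with *count obtained for the scheduled treatment day*. Note that the worst-toxicity heading does not apply to these rows. Keep the neutropenic-fever row as the only nadir-based reduction.
- **(b) Caption and heading.** Make them agree by stating that the grid applies to both day 1 and day 15.
- **(c) Counts that trigger a hold.** State whether such a count also lowers the dose on restart. This is a clinical choice that the current text does not settle, and it should be disclosed as one. Reading the section 7.4 hold rule as applying to day 1 of each cycle, an ANC below 1,500 is held until it reaches 1,200. If hold counts do not reduce the dose, the grade 3 and 4 neutropenia rows have little effect on day 1. This assumes those grades lie below 1,200; the protocol cites CTCAE 4.0 without reproducing its cut-offs.
- **(d) Panitumumab.** In the section 7.5 re-escalation bullet, change 60% to 50% to match Table 3.

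The cost is the amendment and the clinical decision in (c); no visit or test is added. The downside is that a patient whose afebrile grade 3 or 4 interim count has recovered by the treatment day is not reduced. The nadir sentence already says this, but the clinical team should accept it knowingly. If they prefer the worst-count rule, the nadir sentence and the treatment-day bullet should both go, and an interim count after each dose should be scheduled so that dosing does not hinge on chance draws. Section 11.1 shows that patients were enrolled under a previous version, so the amendment should say from which treatment the rule applies.

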Interruption of Panitumumab Infusion

Subjects who experience any serious infusion reaction during panitumumab administration will have the infusion stopped. Continuation of dosing will be based on the severity and resolution of the event and will be at the discretion of the investigator. Suspected infusion reactions should be reported as an adverse event. All subjects who experience such an event will be followed for safety.

Toxicity Assessment

Toxicities will be recorded as adverse events on the Adverse Event case report form and must be graded using The National Cancer Institute's Common Toxicity Criteria (CTCAE) version 4.0 (Appendix 4), with the exception of skin- or nail-related toxicities, which must be graded using CTCAE version 3.0 with modifications (see Appendix 4a).

Panitumumab Dosage Adjustments

For subjects who experience toxicities while on study, one or more doses of panitumumab may need to be withheld, reduced, or delayed (administered at > 14 day intervals). On resolution of toxicity, a limited number of attempts to re-escalate reduced panitumumab doses will be allowed (outlined in Figure 4). Dose escalations above 6 mg/kg starting dose are not allowed. Panitumumab dose reductions are listed in Table 3.

Table 3. Panitumumab Dose Reductions

	Starting Dose	1 st Dose Reduction	2 nd Dose Reduction
Percentage (%)	100	80	50
mg/kg	6	4.8	3.0

Criteria for Withholding a Dose of Panitumumab

Skin- or nail-related toxicities:

- Symptomatic skin- or nail-related toxicity requiring narcotics, systemic steroids, or felt to be intolerable by the subject
- Skin or nail infection requiring IV antibiotic or IV antifungal treatment
- Need for surgical debridement
- Any skin- or nail-related serious adverse event

Non-skin- or nail-related toxicities:

Any grade 3 or 4 toxicity with the following exceptions:

- Panitumumab will only be withheld for symptomatic hypomagnesemia and/or hypocalcemia that persists despite aggressive magnesium and/or calcium replacement
- Panitumumab will only be withheld for grade 3 or 4 nausea, diarrhea, or vomiting that persists despite maximum supportive care (see Section 6.6 and 6.7.1 for diarrhea management guidelines)
- Panitumumab will only be withheld for grade ≥ 3 anemia or grade 4 thrombocytopenia that can not be managed by transfusion(s) or cytokine therapy

Criteria for Re-treatment with Panitumumab

Skin- or nail-related toxicities:

- Panitumumab administration may recommence once:

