- The adverse event has improved to \leq Grade 2 or returned to baseline, and;
- The subject has recovered to the point where symptomatic skin- or nail-related toxicity is felt to be tolerable; and,
- Systemic steroids are no longer required, and
- IV antibiotic or IV antifungal treatment is no longer required

Non-skin- or nail-related toxicities:

- Panitumumab administration may recommence once the adverse event has improved to \leq Grade 1 or returned to baseline.

Dose Modification Schedule

- Subjects should be assessed for toxicity before each dose. Dose modification should be performed according to the schedule described below and outlined in Figure 1.

- Subjects who develop a toxicity that does not meet the criteria for withholding a dose of panitumumab (Section 6.5) should continue to receive panitumumab and their symptoms should be treated.
- Panitumumab-related toxicity will be considered resolved if it improves to a degree that allows for re-treatment with panitumumab (Section 6.5).
- For subjects who experience a toxicity that meets the criteria for withholding a dose of panitumumab:
 - Subjects receiving either 100% or 80% of the starting dose of panitumumab are allowed to have up to 2 subsequent doses withheld for toxicity. The second dose should only be withheld if the toxicity has not resolved by the time that the subsequent dose is due. Subjects treated at the 100% dose level whose toxicity resolves after 1 dose of panitumumab is withheld should be re-started at the 100% dose level (recommended but not required, reduction to the 80% dose is allowed as an alternative to re-challenge with the 100% dose).
 - If toxicity recurs, subjects treated at the 100% dose or 80% dose should be re-started at the 80% dose or 50% dose, respectively, when the toxicity resolves after withholding 1 or 2 doses of panitumumab.
 - Subjects treated at the 100% dose level whose toxicity resolves only after 2 subsequent doses of panitumumab are withheld should be re-started at the 80% dose level.
 - Subjects treated at the 80% dose level whose toxicity resolves after withholding 1 or 2 doses of panitumumab should be re-started at the 50% dose level.
 - Subjects who experience toxicity at the 50% dose level will not be re-treated with panitumumab.

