It is recommended that panitumumab doses will be escalated in subjects whose toxicity resolves to the degree that meets the criteria for re-starting a dose of panitumumab (Section 6.5). Dose escalations are recommended but not required. Dose escalations should occur in the following manner:

- Subjects treated at the 80% dose level whose toxicity does not recur should receive the 100% dose level at the next dose unless a previous attempt to re-escalate to the 100% dose level was not tolerated (re-initiation of the 80% dose is allowed as an alternative to dose escalation).
- Subjects treated at the 50% dose level whose toxicity does not recur should receive the 80% dose at the next dose unless a previous attempt to re-escalate to the 80% dose level was not tolerated (re-initiation of the 60% dose is allowed as an alternative to dose escalation).
- Subjects who miss 3 or more consecutive scheduled doses due to toxicity or are unable to receive a dose of panitumumab within 6 weeks of having received their previous dose of panitumumab due to toxicity will be considered unable to tolerate panitumumab and will not be retreated with panitumumab.
- In case of unexplained respiratory symptoms such as non-productive cough, dyspnea, crackles, or radiological pulmonary infiltrates, panitumumab should be discontinued until further pulmonary investigation

Panitumumab Delayed- or Missed-Doses

Panitumumab should be administered by IV infusion on the first day of each treatment cycle. However, if panitumumab dose cannot be administered as scheduled, every attempt should be made to administer the drug within 3 days of the scheduled dose (up to 3 days before the scheduled dose or up to 3 days after the scheduled dose). If it is necessary to change a subject's visit from the originally scheduled date, the subsequent visits should continue at the previously scheduled days/dates. If the dose is not administered within the \pm 3-day window, the dose will be considered a missed dose, and the next scheduled dose should be given at the time of the regularly scheduled dose. Missed doses will not be made up.

Discontinuation of Panitumumab

Panitumumab will be administered until subjects are unable to tolerate panitumumab, disease progression, death, or study withdrawal by the subject, investigator, or sponsor

[figure not shown]
Electrolyte Management

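### Section 7.5 leaves panitumumab dosing after any serious infusion reaction to the investigator, with no exception for the anaphylactic and severe or life-threatening reactions that Section 7.6 takes off treatment, and nothing says that 7.6 governs

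*Combined protocol and SAP*

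**What the plan says.** Three parts of Section 7.5 bear on dosing after an infusion reaction.

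- **Interruption of Panitumumab Infusion:** "Subjects who experience any serious infusion reaction during panitumumab administration will have the infusion stopped". The next sentence is "Continuation of dosing will be based on the severity and resolution of the event and will be at the discretion of the investigator". No type or grade of reaction is excepted.
- **Pre-medication for Panitumumab:** "If, during or after any infusion, a reaction occurs, pre-medication may be used for subsequent panitumumab infusions", following institutional guidance or the investigator's judgement. No severity limit is given.
- **Withholding and re-treatment, non-skin toxicity:** a dose is withheld for "Any grade 3 or 4 toxicity with the following exceptions", and infusion reactions are not among the exceptions. For re-treatment, "Panitumumab administration may recommence once the adverse event has improved to" grade 1 or lower, or has returned to baseline. Infusion reactions are not excluded here either.

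Section 7.6 (Infusion-Related Toxicity and Hypersensitivity) is graded by severity. Mild reactions: finish the infusion under supervision. Moderate: stop, treat, resume slowly, and remove the patient from protocol therapy if symptoms return. Severe life-threatening (the examples include angioedema and hypotension needing pressors): stop, treat, and remove the patient from protocol therapy. It also requires therapy to be discontinued for anaphylaxis and calls panitumumab contraindicated after a life-threatening hypersensitivity reaction to it.

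The only pointer in 7.5 that could mean 7.6 is "see Section 6.6 and 6.7.1 for diarrhea management guidelines". It concerns diarrhea only and appears to use old numbering, because the current Section 6.6 is Efficacy Parameters.

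**The concern.** For anaphylaxis and for severe or life-threatening reactions, one section gives the investigator a choice and the next gives none. Section 7.5 is the panitumumab dose-modification section, so it is where a site would naturally look when deciding whether to dose again. Section 9 counts a life-threatening event as serious, so such a reaction falls squarely under the discretion sentence.

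What is at stake is patient safety and uniform conduct across the participating institutions. Section 1.2.1.5 reports fatal infusion reactions, and fatal reactions in patients who had earlier hypersensitivity to panitumumab. Giving the drug again to such a patient is what 7.5, read alone, would allow.

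**Working it through.** The plan states no figure on this point, so the main check is a comparison of the two sections by type of reaction.

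| Reaction | Section 7.5 | Section 7.6 | Consistent? |
|---|---|---|---|
| Mild | No stop unless serious; pre-medication optional later | Complete the infusion | Yes |
| Moderate | Discretion if serious | Slow resumption; removal on recurrence | No clear conflict |
| Severe / life-threatening | Discretion | Removal from protocol therapy | No |
| Anaphylaxis | Discretion | Discontinue therapy | No |

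The mismatch is confined to the last two rows.

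**Does other text close the gap?**

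- The Section 7.5 stopping rules do not name infusion reactions. They cover toxicity at the 50% dose, three or more consecutive missed doses or no dose within 6 weeks (such patients "will be considered unable to tolerate panitumumab and will not be retreated with panitumumab"), general intolerance, progression, death and withdrawal. There is also a hold for unexplained respiratory symptoms, but it lasts only until pulmonary investigation.
- The Section 6.8 withdrawal list does not name infusion reactions. Its toxicity item rests on the treating physician's opinion.
- Section 4.1 item 11 and Section 4.2 item 13 exclude earlier severe reactions or known sensitivity. They apply at entry, not to a reaction on study.
- No sentence ranks 7.6 above 7.5.

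**How often could it arise?**

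Inputs: n = 25 (Sections 3.2 and 10.1); severe or grade 3 and higher potential infusion reactions under 1% (Sections 1.2.1.5 and 1.2.1.6, monotherapy). I use p = 0.01 as the ceiling and p = 0.005 as an assumed lower value.

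- Expected number = n × p: 25 × 0.01 = 0.25; 25 × 0.005 = 0.125.
- Chance of at least one = 1 − (1 − p)^25: 1 − 0.99^25 = 0.222; 1 − 0.995^25 = 0.118.

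These are chances of a reaction, not of wrongful re-dosing. The latter needs the share r of affected patients who would be re-dosed, which the documents do not give. As illustration only, 1 − (1 − p·r)^25 at p = 0.01 gives 1.2% for r = 5% and 11.8% for r = 50%. At p = 0.005 it gives 0.6% and 6.1%.

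The 1% figure is a proxy. The definition in Section 1.2.1.5 counts chills, fever and dyspnea, so it is broader than anaphylaxis or a life-threatening reaction. It covers only the 24 hours after the first dose, so it may miss later infusions. No rate is given for panitumumab with FOLFIRI.

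**The case against.** The best reply is that this is a missing cross-reference, not a pair of rules that cannot both be obeyed. The discretion sentence makes continuation depend on severity, and the very next section supplies the severity tiers. The 7.5 language is mostly permissive and the 7.6 language is mandatory, so a careful reader follows 7.6. The entry criteria show the same intent. This stands, and it limits the point to an inconsistency. It does not remove it, because the precedence is left for each reader to infer.

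A second reply is that central review would catch a problem. Section 9 has subsites report every serious adverse event to the lead investigator and coordinator within 24 hours, and the sponsor medically reviews all of them. The next dose is due 14 days later. This is real protection against a later re-dose. It does not cover resumption on the same day, and it depends on the event being classed as serious.

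A reader might also infer that 7.5 directs a full-dose restart after a severe reaction, because the dose schedule says that patients at 100% "whose toxicity resolves after 1 dose of panitumumab is withheld should be re-started at the 100% dose level". The documents do not support this. That rule applies after a dose has been withheld, and a reaction that clears before the next scheduled dose need not lead to one. Section 7.5 treats infusion reactions in a subsection of their own, so applying the general schedule to them is an inference. The sentence is also marked as recommended, not required.

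**Conclusion.** The inconsistency is real but narrow. For anaphylaxis and severe or life-threatening infusion reactions, 7.5 grants a discretion that 7.6 withholds, and the protocol does not say which prevails. It would be too strong to say that the protocol instructs re-dosing or that the sections are irreconcilable.

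The frequency is low: at most about 0.25 expected reactions in 25 patients, and at most about a 22% chance of seeing even one, if the monotherapy ceiling of 1% applies to this combination. The probability of wrongful re-dosing is smaller and cannot be estimated from the documents. There is no effect on PFS, power or type I error. The case for correction rests on a possibly fatal outcome, which the protocol itself documents for earlier hypersensitivity, set against a very small cost.

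**What to change.** In Section 7.5, Interruption of Panitumumab Infusion, replace the discretion sentence with:

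> Infusion reactions are managed by the severity tiers in Section 7.6, which governs. After anaphylaxis or severe/life-threatening symptoms the patient is removed from protocol therapy and receives no further panitumumab; for other reactions, continuation is at the investigator's discretion within the Section 7.6 tiers.

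Add to both the non-skin re-treatment criterion and the pre-medication sentence:

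> except anaphylaxis or severe/life-threatening infusion reactions (see 7.6)

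The wording names removal from protocol therapy as well as the end of panitumumab. A bar on panitumumab alone would be narrower than 7.6 and would leave open whether FOLFIRI continues.

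The cost is amendment wording and a notice to sites.
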